
	
retrospective study] that doesn't affect this study's efficacy and safety as determined by the investigator.)
 
[Laboratory tests]
 
12) At screening, those who had
 
 ① serum alanine aminotransferase (ALT), aspartate aminotransferase (AST), or total bilirubin levels ≥ 2 X upper limit of normal ② serum creatinine or BUN ≥ 2 X upper limit of normal 
[Others]
 
13) Pregnant or breast-feeding women
 
14) Those who do not consent to use appropriate contraceptive methods during the study.
 
 - Appropriate contraceptive methods for patients or their partners - For Male subject: to use barrier method such as male condom and surgical sterilization such as vasectomy - For Female subject: to use 1) hormonal contraceptive such as Intrauterine system : intrauterine hormone-containing system, implant, injection, contraceptive pills, or 2) non hormonal contraceptive such as Intrauterine system : copper loop, barrier method : female condom, diaphragm or cervical cap, or surgical sterilization : tubectomy. 
15) In the opinion of the investigator, those who were unsuitable for any reason.

Investigational product and mode of administration	
[Investigational Product]
 
 ● Study drug: Fexuprazan tablet 40 mg ● Control drug: Esomeprazole capsule 40 mg 
[Treatment period]
 
 ● Treatment 1: 4 weeks A dose of Study drug or Control drug will be administered orally once daily without regard to meals for 4 weeks. The timing of administration should be kept consistent for each subject. ● Treatment 2: Up to 8 weeks (4 weeks + 4 weeks) Patients who have not been healed after the Treatment 1 of investigational product administration will have an additional 4-weeks of treatment period (Treatment 2) with the same mode of administration. Patients that categorized as a non-healed are those with a GERD-Q score >8.

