1.4 Prior Study Results

1) Phase 1 Study (DW_FEXUPRAZAN001)

A first in human study (FIH) in Korea was conducted in healthy male volunteers. In a single ascending dose study (n = 72), a single dose of 10, 20, 40, 80, 160, and 320 mg of Fexuprazan was administered in a fasted state with its corresponding dose of placebo in a double-blind manner to assess the safety, tolerability, and pharmacokinetics/pharmacodynamics and 20 and 40 mg of Esomeprazole were used as an active control to compare pharmacodynamic results with Fexuprazan.

To determine the impact of food, 160 mg was studied in a single dose and crossover study. No clinically significant change was found in physical examination, laboratory tests, vital signs, and electrocardiogram, the safety and tolerability endpoints. No SAE occurred and all AEs that occurred were mild (CTCAE 4.0 grade = 1) and were recovered without any special

treatment. A total of 7 adverse drug reactions (ADRs) with suspected causal relationship to Fexuprazan occurred which were epigastric discomfort, dyspepsia, and nausea (1 case each); vomiting and headache (2 cases each). Pharmacokinetic exposure of Fexuprazan oral administration increased more than dose proportionally (Supra-proportionality). In the assessment of pharmacodynamics based on the measurements of intragastric pH for 24 hours after administration of the investigational product, acid secretion within the stomach was inhibited more rapidly after a single administration of Fexuprazan than PPI, and the time during which intragastric pH remained ≥ 4 increased with dose escalation, indicating that gastric acid secretion inhibitory effect continued until nighttime with once-daily dosing. When administering Fexuprazan 160 mg before/after meal, no significant pharmacokinetic/pharmacodynamic change caused by food was observed.

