In 7-day multiple ascending dose study (n = 48) conducted at doses of 20, 40, 80, and 160 mg after the single dose study, the safety and tolerability were confirmed for all doses. No SAE occurred and all AEs that occurred were mild (CTCAE 4.0 grade = 1) and were recovered without any special treatment. A total of 6 ADRs that were suspected to be causally related to Fexuprazan occurred which were abdominal distension, abdominal pain, skin exfoliation, headache, abdominal discomfort, and blood creatine phosphokinase increased (1 case each). After multiple doses of Fexuprazan during 7 days, the pharmacokinetic exposure increased dose-proportionally and the accumulation ratios resulting from multiple dosing were $C_{max} = 0.91$ to 1.24 and $AUC_{tau} = 0.93$ to 1.47 . In the pharmacodynamic assessment, the percentage of time during which pH remained ≥ 4 in 24 hours was slightly increased after multiple dosing compared to single dosing, and Fexuprazan 40 mg showed the equivalent level of pharmacodynamics as Esomeprazole 40 mg.

2) Phase 2 Study (DW_FEXUPRAZAN002)

A multi-center, randomized, double-blind, active-controlled, phase 2, therapeutic exploratory study was conducted to evaluate the efficacy and safety of Fexuprazan by dose in patients with erosive gastroesophageal reflux disease in Korea.

In a total of 211 subjects, the results of having administered Fexuprazan 20 mg, 40 mg, 80 mg or Esomeprazole 40 mg once daily before meals for up to 8 weeks were as follows.

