1.5 Assessment of Benefits and Risks

Reportedly, PPIs, the first-line therapy for diseases related to gastric acid secretion, takes 3 days or longer to make improvements in major symptoms (acid regurgitation and heartburn)⁸; their acid secretion inhibitory effects do not last until the nighttime¹⁰; and the genetic polymorphism of CYP2C19¹¹ causes variations in individual efficacy. Moreover, the regimen is restricted to be taken before a meal. Currently, drugs with APA mechanism are being developed to overcome these limitations of PPIs. The first phase I clinical study in healthy male adults confirmed that, unlike other PPIs that are activated under a strong acidic condition, Fexuprazan had a fast onset time and showed its acid secretion inhibitory effect that persisted until the nighttime since it had a reversible mechanism of action without activation by inhibiting the proton pump. Besides, since food does not have any significant effect on absorption of the drug, the patients can take the drug with or without having a meal, and it is expected that the patient's convenience of taking the drug can be improved.

[figure not shown]
In the phase 2 study conducted in patients with erosive gastroesophageal reflux disease, healing of mucosal breaks in all Fexuprazan groups was non-inferior to the Esomeprazole 40 mg group, and no AE and ADR was noticeable in terms of safety. Also, Fexuprazan showed an effect of alleviating acid regurgitation and heartburn which are the major symptoms of gastroesophageal reflux disease during the treatment period.

Thus, the benefit expected from administration of Fexuprazan in patients with erosive gastroesophageal reflux disease, one of gastric acid secretion related diseases is considered to outweigh the risk, and a multi-center, randomized, double-blinded, active-controlled, phase 3, therapeutic confirmatory study was planned to assess the efficacy and safety of Fexuprazan in patients diagnosed with erosive gastroesophageal reflux disease.

[figure not shown]

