7.2.2 Administration Method

For maximum 8 weeks from the next day of investigational product dispensing, 1 tablet/capsule will be administered orally once daily without regard to meals. Tablets/Capsules should be taken at a regular time.

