7.3.3 Treatment Compliance

In order to ensure the validity of research data related to the ability of IP to relieve symptoms and ensure safety in subjects, also to gain a better understanding of drug performance in real-world settings and improve the quality of study outcomes, at each visit after the administration of the IP, all subjects should return the unused IP prescribed at the previous visit and empty packaging, and the sub-investigator (or a designee) will check the number of tablets/capsule to be taken, number of tablets/capsules actually taken, and number of returned and unreturned tablets/capsules and record them on the case report form at each visit.

$$\text{Treatment compliance (\%)} = \frac{\text{Number of tablets/capsules actually taken}}{\text{Number of tablets/capsules to be taken}} \times 100$$

8 Study

Procedures and Assessments

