2	Sedang	Sedikit ketidaknyamanan dan sedikit keterbatasan dalam aktivitas normal sehari-hari
3	Berat	Gejala sering dirasakan, dan sering terjadi keterbatasan dalam aktivitas normal sehari-hari
4	Sangat Berat	Gejala yang terus menerus dan keterbatasan yang signifikan terhadap aktivitas normal sehari-hari

Penilaian gejala “malam hari” (waktu tidur)

0	Tidak ada	Tidak ada gejala
1	Ringan	Gejalanya terasa, namun bisa diabaikan dan tidak mengganggu tidur
2	Sedang	Sedikit ketidaknyamanan, sedikit gangguan pada tidur
3	Berat	Gejalanya sering dirasakan, dan sering terjadi gangguan tidur
4	Sangat Berat	Gejalanya dirasakan terus menerus, dan sulit tidur

– Perhatian –

- ✓ Gunakan pulpen berwarna hitam jika memungkinkan, dan saat mengubah isi, coret area yang perlu diperbaiki dengan garis lurus, tulis perbaikannya, tanggal dilakukan perbaikan, alasan perbaikan, dan kemudian tandatangani. Harap gunakan tanda tangan yang sama dengan tanda tangan di sampul buku.

Contoh) **LAR** LAK 16/04/2017, salah tulis, (tanda tangan)

- ✓ Obat penelitian harus diminum sekali sehari tanpa mempertimbangkan waktu makan dan sebaiknya diminum pada waktu yang tetap. Mohon cantumkan di buku harian subjek jika Anda sudah mengonsumsinya. Pada kunjungan berikutnya, Anda harus mengembalikan kotak obat, sisa obat yang belum digunakan, dan kemasan obat yang sudah kosong.
- ✓ Saat kunjungan berikutnya, pastikan untuk membawa formulir aplikasi Anda.
- ✓ Kami meminta kerjasama Anda dengan staf medis hingga akhir studi ini. Jika Anda mengalami ketidaknyamanan atau kejadian yang tidak diharapkan selama periode uji klinis, mohon beri tahu staf medis penelitian.

Peneliti atau perawat penelitian	Kontak

Hari ke- ()		Tanggal:	Bulan:	Tahun:	
Apakah Anda sudah mengonsumsi obat investigasi uji klinis?					
 Siang hari (diisi sebelum tidur di malam hari)		 Malam hari (diisi setelah bangun tidur di pagi hari)			
Nyeri ulu hati	 Tidak ada  Ringan  Sedang  Berat  Sangat berat		Nyeri ulu hati	 Tidak ada  Ringan  Sedang  Berat  Sangat berat	

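### The esomeprazole control is dosed without regard to meals with no reason given, although Section 1.5 says the PPI regimen is tied to a meal: a low-severity point, cheap to settle

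*Combined protocol and SAP*

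**What the plan says.** **Dosing instruction.** The synopsis states "A dose of Study drug or Control drug will be administered orally once daily without regard to meals for 4 weeks" and asks that each subject keep to a consistent time. Section 7.2.2 says "1 tablet/capsule will be administered orally once daily without regard to meals"; Sections 6.2 and 8.3.13 carry the same instruction. The capsule is esomeprazole, so the control is explicitly covered. The diary in Attachment 4 tells subjects in Indonesian: "Obat penelitian harus diminum sekali sehari tanpa mempertimbangkan waktu makan" (the study drug is to be taken once a day without considering mealtimes).

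**What the protocol says about PPIs and meals.** Section 1.5 lists limitations of PPIs, among them: "Moreover, the regimen is restricted to be taken before a meal".

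**Earlier head-to-head dosing.** Section 1.4 reports that the phase 2 study gave all fexuprazan doses and esomeprazole 40 mg "once daily before meals for up to 8 weeks".

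**Food data.** Section 1.4 says of the phase 1 study: "To determine the impact of food, 160 mg was studied in a single dose and crossover study". That is fexuprazan in healthy men. Section 13.8.1 also lists reactions at 80 mg fasting and fed, again fexuprazan. Section 1.5 draws the with-or-without-food conclusion for fexuprazan only.

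**Rationale for the control.** Section 4.3.3 justifies the once-daily interval and does not mention meals. Section 6.1.2 gives the control's product name, form, content and storage.

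**What is recorded.** Section 7.3.3 bases compliance on counts, including the "number of tablets/capsules actually taken, and number of returned and unreturned tablets/capsules". The daily diary page asks "Apakah Anda sudah mengonsumsi obat investigasi uji klinis" (whether the drug has been taken).

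**The concern.** The primary claim is non-inferiority of fexuprazan to esomeprazole at a margin of 10 percentage points (Sections 9.3 and 9.4.2). In such a trial, anything that lowers the control response makes the claim easier to reach. A reader who sees the remark in Section 1.5 beside the dosing instruction will ask whether esomeprazole was given as it should be. The protocol offers no answer, because its food rationale stops at fexuprazan.

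The possible bias runs both ways. If meal-free dosing lowers the fexuprazan response instead, it works against the claim. Meal-free fexuprazan 40 mg in patients is not directly shown either: the food crossover used 160 mg in healthy men, and the phase 2 patients took it before meals.

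**Working it through.** **Step 1: the texts side by side.**

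| Question | Fexuprazan | Esomeprazole |
|---|---|---|
| Instruction in this trial | Regardless of meals | Regardless of meals |
| Phase 2 dosing (1.4) | Before meals | Before meals |
| Food data in the protocol | 160 mg crossover; 80 mg fasting/fed listing of reactions | None |
| Statement on meals (1.5) | With or without food | Class remark: before a meal |
| Reason for meal-free dosing | Given (1.5) | None |

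The gap is in the right-hand column: a meal condition is stated for the class, not applied to the control, and the change is not explained.

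**Step 2: the plan's own sample size.** Inputs from Section 9.4.2: control 0.885, study drug 0.940, margin 0.1, one-sided 2.5%, 53 per group, 20% dropout.

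- Mean rate: (0.885 + 0.940)/2 = 0.9125.
- Pooled SE: √(2 × 0.9125 × 0.0875/53) = 0.05489.
- Unpooled SE: √(0.885 × 0.115/53 + 0.940 × 0.060/53) = 0.05463.
- Power: Φ[(0.055 + 0.100 − 1.960 × 0.05489)/0.05463] = Φ(0.868) = 0.807, matching the stated 0.80729.
- Dropout: 53/0.8 = 66.25, rounded up to 67 per arm, 134 in total, as stated.

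The sample size is not in dispute, and the fix does not alter it.

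**Step 3: illustration of what a control loss would do.** Two inputs here are assumptions. One is the size of the loss. The other is that 88.5% is a before-meal rate; Section 9.4.2 attaches no meal condition to that figure. The control rate is 88.5% minus a loss of 0, 1, 2.5 or 5 points, that is 88.5%, 87.5%, 86.0% or 83.5%. The chance of a claim is the sum, over all pairs of responder counts with 53 per arm, of the binomial probabilities for which the lower two-sided 95% bound exceeds −0.1. Sections 9.2.3.1 and 9.3 name tests but no interval method for the difference, so two are shown.

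| Assumed control loss (points) | Study drug 78.5%: Miettinen-Nurminen | Study drug 78.5%: Wald | Study drug 94.0%: Miettinen-Nurminen | Study drug 94.0%: Wald |
|---|---|---|---|---|
| 0 | 2.5% | 3.1% | 77% | 83% |
| 1 | 3.4% | 4.1% | 81% | 85% |
| 2.5 | 5.2% | 6.1% | 86% | 89% |
| 5 | 9.5% | 10.9% | 92% | 94% |

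The 78.5% case puts fexuprazan exactly 10 points below a control at 88.5%. The 94.0% case uses the protocol's planning rate; there fexuprazan really is better, so the claim is correct and the loss does no harm to it.

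**The case against.** The strongest reply is that the deciding fact lies outside the documents. The approved instruction for the control product named in Section 6.1.2 is not reproduced. If it permits dosing without regard to food, all that remains is a missing sentence in Section 4.3.3. This stands, and it is why the fix begins with that instruction.

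The internal evidence is also thin. The sentence in Section 1.5 is an uncited background remark about a class. The same section ends by describing a double-blind phase 3 study in erosive disease, which is not this open-label trial, so the text may have been carried over. Phase 2 dosed fexuprazan before meals too, so it shows uniform administration, not a need specific to esomeprazole. Both points stand. They limit the weight of the inconsistency but do not explain it.

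Identical instructions in both arms are a legitimate choice, and the synopsis does ask for consistent timing. But identical wording is neutral only if neither drug depends on meals, and the protocol argues that for fexuprazan alone. Consistent timing does not fix how the dose relates to a meal.

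A reader might infer that the trial under-treats its control or that its type I error is inflated. The documents support neither. No meal effect on esomeprazole is reported, and the error rate for the hypothesis as written, which compares the drugs as dosed here, is unaffected. Nor do they establish that meal timing goes uncaptured: that reading rests on the protocol and the diary form, and the eCRF and its completion guidelines are not available.

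**Conclusion.** A cheap improvement of low severity. The text shows an unexplained departure: meal-free dosing of the control beside a class-level statement that the regimen belongs before a meal, with a food rationale for the study drug only. The direction of concern is clear only on a condition: if meal-free dosing weakens esomeprazole, non-inferiority becomes easier to claim.

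No size can be given from the documents, and zero is possible. The 3.4% to 9.5% range (score interval, losses of 1 to 5 points) rests on an assumed loss, on reading 88.5% as a before-meal rate, and on fexuprazan being truly 10 points worse than that control. It illustrates sensitivity and does not estimate bias in this trial.

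**What to change.** 1. Check the approved instruction of the control product in Section 6.1.2.
2. If it allows dosing regardless of meals, keep the present instruction and cite the source in Section 4.3.3. The cost is about one sentence.
3. If it does not, revise the synopsis, Sections 6.2, 7.2.2 and 8.3.13, and the control-arm diary to say: esomeprazole, one capsule once a day before a meal, at the interval the approved instruction gives; fexuprazan, one tablet once a day, with or without food; keep the time of day the same. State in Section 13.5 that missed meal timing is not a major deviation. The last item there is open-ended, and Section 9.2.1 makes the PPS the primary analysis set, so silence could remove patients from it.

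A daily diary tick for dose before a meal is optional. It would be descriptive only: timing within an arm is self-selected, so it cannot size a meal effect, and the question is ambiguous unless an interval is given.

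**Cost of step 3.** One amendment with signed consent of all parties and IRB approval. Section 11.10 limits amendments after initiation to exceptional cases, so it is best made before enrolment. Instructions would differ slightly between arms in a trial that is already open label. Sample size, visits and the primary analysis stay as they are.

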Study Methodology	
Subjects will be provided a written informed consent to participate in the study and then undergo any screening. If a subject is taking any drug that affects the gastric mucosa at the time of screening, the treatment will be start after washout period of up to 2 weeks. Subjects who meet all of the inclusion criteria and none of the exclusion criteria based on the screening test results will be randomized.
 
Overall, the subjects will receive treatment for a duration of 4 ~ 8 weeks., The subjects will take 1 tablet/capsule of the investigational product (IP) once daily (1 tablet of Fexuprazan 40 mg or 1 capsule Esomeprazole 40 mg according to randomization). Initially, the subject will received the IP for 1 week at Visit 2 (Day 0). Subject will visit the study site at Visit 3 (Day 7 ± 5 days) for early evaluation and will be prescribed for another 3 weeks of IP. Subjects will visit the study site at Visit 4 (Day 28 ± 5 days) to determine healing status through symptom relief. Healed subjects after 4 weeks of treatment will have a Safety Follow-Up (F/U) visit after 2 weeks, while unhealed subjects will continue with an additional 4 weeks of treatment. After unhealed subjects have completed a total of 8 weeks of treatment at Visit 5 (Day 56 ± 5 days), they will have a Safety F/U visit after 2 weeks. (This Safety F/U will be conducted over the phone. If necessary, additional examination and treatment may be performed according to the investigator's judgment.)

Figure 1. Study Schematic

Inclusion Criteria	
Subjects must meet all the following criteria:
 
 1) Male and female adults aged 18 to 60 years at the date of the written informed consent form. 2) Those who had experienced heartburn and/or acid regurgitation confirmed with: 
 ➢ GERD-Q Score >7 and ➢ People who have experienced heartburn symptoms > 3 days within the last 7 days, or ➢ People who have experienced acid reflux (symptom of acid reflux or back flowing of contents from stomach into the esophagus) > 3 days within the last 7 days 3) Those who could understand the provided information and able to fill out the questionnaire and subject diary. 4) Those who voluntarily decided to participate in the study and wrote the informed consent form.

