Efficacy Endpoints	
[Primary efficacy endpoints]
 
 1. Proportions of subjects with symptoms relief at week 4 measured by GERD-Q Score <8 
[Secondary efficacy endpoints]
 
 1. Proportions of subjects with symptoms relief at week 8 measured by GERD-Q Score <8 (Week 8 evaluation will only be applicable to patient receiving treatment 2) 2. Assessment on symptoms based on the diary of subjects 
 - The day to reach complete response (disappearance of heartburn, acid regurgitation, or heartburn/acid regurgitation for 7 consecutive days) after the first IP administration. - Proportions of subjects without the major symptoms (heartburn, acid regurgitation, or heartburn/acid regurgitation) for first 7 days, 4 weeks, and 8 weeks after the first IP administration. - Proportions of days free of major symptoms (heartburn, acid regurgitation, or heartburn/acid regurgitation) for first 7 days, 4 weeks, and 8 weeks after the first IP administration (including all daytime, nighttime, and daytime/nighttime) 3. Assessment on symptoms of reflux disease (GERD-Q) 
 - Changes from baseline in frequency by major symptom after 7 days, 4 weeks and 8 weeks. 4. Assessment of Quality of Life (GERD-HRQL: GERD-Health related quality life) 
 - Changes from baseline in the total score of GERD-HRQL after 7 days, 4 weeks and 8 weeks. (Week 8 evaluation will only be applicable to patient receiving treatment 2) 
[Exploratory endpoints]
 
Assessment on symptoms based on the diary of subjects.
 
 - Proportions of subjects who have not been awakened during sleep for heartburn or acid regurgitation for first 3 days, 7 days, 4 weeks, and 8 weeks (or based on the day Investigator's need) after the first IP administration.

	
 - Proportions of subjects who have relieved from chronic cough for first 3 days, 7 days, 4 weeks, and 8 weeks (or based on the day Investigator's need) after the first IP administration daytime and nighttime. - Proportions of subjects who have relieved from irritating feeling in the throat for full 3 days, 7 days, 4 weeks, and 8 weeks (or based on the day Investigator's need) after the first IP administration daytime and nighttime. 
(Week 8 evaluation will only be applicable to patient receiving treatment 2)

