- 8) Pregnancy test will be performed with serum or urine pregnancy test will be performed at Visit 1. (Women who medically do not have child-bearing potential are exempt from the pregnancy test). If Visit 1 and Visit 2 are conducted on the same day, another pregnancy test (serum or urine test) should be conducted prior to IP administration even if the test result within 2 weeks before the date is available.
- 9) Eligibility of subjects will be assessed based on the results from Visit 2 (However GERD-Q result from Visit 1 will be used as the eligibility criteria).
- 10) Subjects who have not symptoms relief at Visit 4 will be prescribed the investigational product for treatment 2, and subject diary will be distributed to them. At Visit 5, treatment compliance will be checked, and subject diary will be collected only from those who have undergone Treatment 2.
(#: Subject diary completion will be checked at Visit 3, and appropriate training on diary keeping will be performed on the phone, if necessary.)
- 11) The Safety F/U will be conducted as a telephone visit within 2 weeks (\pm 5 days) from Last day of Visit 4 and Visit 5 only in subjects who complete all protocol-specific treatments, and the subjects may visit for additional tests or treatments based on the investigator's judgment.
- 12) If a subject decides to discontinue participation or is withdrawn from the study before completion, the Withdrawal visit procedures will take place within 2 weeks from the withdrawal decision. At the Withdrawal visit, the unused IPs or empty packaging will be returned, and the subject diary will be collected. However, assessment of Gastroesophageal Reflux Disease Questionnaire (GERD-Q)^{*)} and quality of life questionnaire (GERD-HRQL)^{*)} must be performed. If the patient refused to visit, above two Questionnaires can be done by telephone call and the document should be written on the EMR by the investigator.
- 13) Subjects who have not been healed after the Treatment 1 of investigational product administration will have an additional 4-weeks of treatment period (Treatment 2) with the same mode of administration.

[Abbreviations and Definition of Terms]

ADR	Adverse drug reaction
AE	Adverse event
AIDS	Acquired immune deficiency syndrome
ALT	Alanine aminotransferase, alanine
ANCOVA	Analysis of Covariance
APA	Acid pump antagonist
AST	Aspartate transaminase, aspartate
ATC	Anatomical therapeutic chemical
BUN	Blood urea nitrogen
BPOM	Indonesia Food and Drug Authority

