4.3 Rationale for Study Design

4.3.1 Rationale for Establishment of Efficacy Endpoints

The clinical study guidelines for gastroesophageal reflux disease treatments requires 4 to 8 weeks of treatment period in general. In Indonesian guideline, Gastroesophageal Reflux Disease (GERD) is diagnosed by GERD Q score > 7 , so the proportion of subject with symptom relief indicator is indicated by GERD-Q < 8 ^[7,12,13]

Also, typical symptoms of gastroesophageal reflux disease are heartburn and acid regurgitation and the clinical study guidelines for gastroesophageal reflux disease treatments specifies to include endpoints for evaluating disappearance of such symptoms. ^[12] Assessment on symptoms includes severity and frequency and, since symptom assessment by physicians or investigators is less reliable, the subjects have to assess their symptoms by themselves.^[12] Given that, this study sets the assessment on symptoms based on the diary of subjects as a secondary efficacy endpoint.

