5.1 Scheduled Completion

If all protocol-specified procedures and assessments are completed after the IP administration, the subject will be considered to have completed the study. Subjects with symptoms relief at Week 4 measured by GERD-Q Score <8 will have the Safety F/U after 2 weeks from the date and be terminated from the study.

In this study, completion of the last subject is defined as the end of study.

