8.1 Visit Schedule

Subjects will provide written informed consent to participate in the study and then undergo any screening. Subjects who meet all of the inclusion criteria and none of the exclusion criteria based on the screening test results will be included into the study. Subjects will have a site visit 1 week after IP administration. Subjects will visit the study site again in person 4 weeks after the first IP administration to determine healing status with symptoms relief at Week 4 measured by GERD-Q Score <8 . Healed subjects will have a Safety F/U visit after 2 weeks (± 5 days) and unhealed subjects will take the IP for additional 4 weeks and then visit the site to determine healing status with symptoms relief at Week 8 measured by GERD-Q Score <8 . The Safety F/U visit will be conducted 2 weeks (± 5 days). The Safety F/U visit will be conducted via telephone visit and subjects will have a visit for additional tests or treatments based on the investigator's judgment.

In the event of withdrawal, the procedures for the Withdrawal visit will also be conducted by visiting the site within 2 weeks after the withdrawal decision is made. See Study Schedule Table for procedures to be performed at each visit.

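### One synopsis sentence gates Treatment 2 at GERD-Q >8, while the rest of the protocol treats a score of 8 as unhealed

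*Combined protocol and SAP*

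**What the plan says.** In the synopsis row on the investigational product, under Treatment 2, patients not healed after the first four weeks receive four more, and the row then puts a number on this: "Patients that categorized as a non-healed are those with a GERD-Q score >8".

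Other places give a different cut-off or imply one:

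- Synopsis, Study Methodology: Visit 4 is held "to determine healing status through symptom relief".
- Synopsis, Efficacy Endpoints, and section 8.4.1.1: "Proportions of subjects with symptoms relief at week 4 measured by GERD-Q Score <8". Section 8.4.2.1 defines relief with the same cut-off.
- Section 4.3.1 starts from the diagnostic score of >7, "so the proportion of subject with symptom relief indicator is indicated by GERD-Q" below 8.
- Section 5.1: "Subjects with symptoms relief at Week 4 measured by GERD-Q Score <8 will have the Safety F/U after 2 weeks".
- Section 8.1: subjects attend "to determine healing status with symptoms relief at Week 4 measured by GERD-Q Score <8", and those unhealed continue for four weeks.
- Schedule of Study Activities, footnote 10: "Subjects who have not symptoms relief at Visit 4 will be prescribed the investigational product for treatment 2". Section 8.3.14 says the same.
- The GERD-Q form in Attachment 2 reads 8–18 as probable GERD.

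The protocol limits Week-8 evaluation to subjects who receive Treatment 2 (synopsis, 8.4.1.2, 9.2.3.2).

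**The concern.** The Visit 4 score decides who is treated for another four weeks and who has Visit 5. The synopsis sentence is the only place that attaches a number to non-healed; elsewhere the reader must infer it as the complement of relief. Someone programming the eCRF or looking up the Treatment 2 gate could therefore take >8 at face value.

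A site that did so would stop treatment in a subject whom footnote 10, 8.1 and 8.3.14 call unhealed. That subject would have no Visit 5 and, on the plain text, would not enter the Week-8 secondary and exploratory outputs. Sites relying on different parts of the protocol would handle identical patients differently. No rationale is given for a separate, higher gate, and it would fit poorly with entry at a score >7: a subject could enrol at 8, still score 8 at Week 4, and not be classed as non-healed.

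**Working it through.** **1. The rules applied to integer scores**

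| Visit 4 score | Relief (<8) | Non-healed, synopsis sentence (>8) | Unhealed, 5.1 / 8.1 / 8.3.14 / footnote 10 |
|---|---|---|---|
| 7 | yes | no | no |
| 8 | no | no | yes |
| 9 | no | yes | yes |

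The rules disagree at one score only. At 8 the subject is neither relieved nor non-healed under the synopsis sentence.

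**2. Is 8 a realistic score?** The form has six items scored 0–3 (total 0–18), and items 3 and 4 are reverse-scored. A subject with no symptoms and no extra medication scores 0+0+3+3+0+0 = 6. Heartburn on 2–3 days adds 2, giving 8. It is also the first score above the relief cut-off.

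**3. The plan's sample size (9.4.2), reproduced for context.** Inputs: 88.5% control, 94.0% study, margin −0.1, one-sided 2.5%, pooled Z-test, n = 53 per group.

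- Mean rate = (0.940 + 0.885)/2 = 0.9125
- Pooled SE = √(2 × 0.9125 × 0.0875/53) = 0.0549
- Unpooled SE = √((0.94 × 0.06 + 0.885 × 0.115)/53) = 0.0546
- Power = Φ((0.055 + 0.1 − 1.96 × pooled SE)/unpooled SE) = 0.80729, matching the plan (0.79984 at n = 52)
- Dropout: 53/0.8 = 66.25, rounded up to 67 per group, 134 in total

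None of these inputs involves the Treatment 2 gate, so correcting the gate leaves the sample size as it is.

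**4. Expected Week-4 non-responders at planning rates**

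| Base | Study | Control | Total |
|---|---|---|---|
| 53 per group, evaluable | 53 × 0.060 = 3.18 | 53 × 0.115 = 6.10 | 9.28 |
| 67 per group, randomised | 67 × 0.060 = 4.02 | 67 × 0.115 = 7.71 | 11.72 |

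**5. Subjects scoring exactly 8.** The documents give no distribution of scores. With an assumed share of 10–50% of non-responders:

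- Evaluable: 0.93 to 4.64 subjects
- Randomised: 1.17 to 5.86 subjects

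**6. Treatment 2 group left under the synopsis sentence, same assumption**

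- Evaluable: 9.28 − 4.64 = 4.64 to 9.28 − 0.93 = 8.35
- Randomised: 11.72 − 5.86 = 5.86 to 11.72 − 1.17 = 10.55
- Study group, across both bases: 3.18 × 0.5 = 1.59 to 4.02 × 0.9 = 3.62
- Control group, across both bases: 6.10 × 0.5 = 3.05 to 7.71 × 0.9 = 6.93

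The group falls from about 9–12 to about 5–11.

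**The case against.** The best reply is that this is a single sentence, out of line even with its own synopsis, and that every operational section already gives the right rule. Harm requires a site or the eCRF to follow that sentence, and the documents do not show that either does. This is fair and limits the weight of the point. It does not remove the conflict: the sentence is current text, it is the only explicit number for non-healed, and the document gives no rule on whether synopsis or body prevails.

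On Week 8, sections 9.2.3.1 and 9.2.3.2 describe relief as cumulative, using the final observation. On that wording a subject last seen at Visit 4 with a score of 8 could stay in the Week-8 relief proportion as not relieved. Section 9.2.1 also allows LOCF for continuous efficacy endpoints other than GERD-HRQL. So exclusion from every Week-8 output is not certain. It does follow from the statement that Week-8 evaluation applies only to Treatment 2 recipients, and in any case no Visit 5 questionnaire or Treatment 2 diary would exist for that subject.

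The count is soft. Without the 10–50% assumption, the number affected lies anywhere from none to all of the expected non-responders. The 11.7 base also ignores dropout before Visit 4.

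Finally, the subject is not abandoned. The safety call may still take place, because footnote 11 provides it "only in subjects who complete all protocol-specific treatments", and section 13.6 provides usual care after the study. Neither replaces the randomised treatment and Visit 5 that footnote 10 and 8.3.14 require.

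**Conclusion.** The concern holds. The synopsis sets the Treatment 2 threshold one point higher than the rest of the protocol, and the two rules give opposite instructions at an attainable score. It is most likely a slip for ≥8 or >7, but it sits on the rule that decides who is treated, so it should be corrected.

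At planning rates about 9 to 12 subjects would be Week-4 non-responders, and about 1 to 6 of them would be affected if 10–50% score exactly 8. That share is assumed. The effect also depends on a site or the eCRF applying the synopsis sentence. It is confined to continued treatment, Visit 5 and the Week-8 outputs; the Week-4 primary endpoint is consistently below 8.

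**What to change.** In the Treatment 2 text of the synopsis, change >8 to ≥8 (equivalently >7), which makes non-healed the exact complement of relief. Program the same rule for Visit 4 in the eCRF: a score of 7 or less goes to completion and Safety F/U under 5.1, and a score of 8 or more goes to Treatment 2 and Visit 5. If any subject has already been handled at a score of 8, list those subjects by arm and site, with the action taken.

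The cost is one symbol and one edit check, with no added patients. On the 10–50% assumption, about 1 to 6 subjects would receive the four further weeks and Visit 5 that footnote 10 and 8.3.14 already require.
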